## Section D: Purpose and Objectives

The purpose of the current proposed study is to pilot test a newly developed strengths-based clinical intervention delivered by diabetes care providers in the context of routine ambulatory diabetes care, designed to promote resilience and support diabetes management among adolescents with T1D and their families. The emphasis of the intervention is shifting the tone of clinical encounters for diabetes care to emphasize and reinforce youths' and families' current strengths and positive diabetes management behaviors. Youth with T1D are seen routinely in clinic every 3-4 months, and this intervention will occur at two consecutive clinic visits. The intervention consists of: (A) assessing youth and family diabetes strengths and adherence prior to each visit, and (B) training diabetes care providers to tailor their clinical encounters around reinforcing each patient and family's unique  $\zeta$ diabetes strengths profile $\zeta$  generated from the strengths and adherence assessments. With its foundation in the Diabetes Resilience Model this intervention focuses on building diabetes resilience by strengthening existing protective behaviors of youth and families and by establishing supportive, patient-centered processes within the healthcare system.

The specific aims of the proposed pilot study are to: Aim 1: Assess the feasibility and acceptability of this strengths-based family intervention. Hypothesis 1A: The intervention will be feasible to conduct in the context of an ambulatory diabetes care clinic and adolescents, families, and providers will report the intervention to be highly acceptable.

Aim 2: Evaluate preliminary intervention impact on clinical outcomes, behavioral diabetes management, and patient satisfaction. Hypothesis 2A: Diabetes regimen adherence will increase and glycemic control will improve (i.e., HbA1c will decrease) from pre- to post-intervention (4-month intervention period). Hypothesis 2B: Adolescents and families will report decreased conflict, decreased diabetes burden, increased diabetes resilience, and increased satisfaction with diabetes care from pre- to post-intervention.

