## **Section F: Design/Procedure**

### **F1. Design**

Select one category that most adequately describes your research:

c) Pilot

Discuss the research design including but not limited to such issues as: probability of group assignment, potential for subject to be randomized to placebo group, use of control subjects, etc.

This pilot study is a single-arm design without a control group. All participants will receive the intervention and will complete baseline and follow-up data. For the purpose of assessing intervention feasibility and acceptability, this design permits more participants to be exposed to the intervention in less time than alternative designs with a wait-list or crossover condition or control group. This will increase the ability to assess participant and provider perceptions about the intervention, to obtain valuable feedback that will help refine the intervention, and to detect any pre-post changes in study outcomes. Following pilot data collection, external funding (NIH R mechanism) will be sought to conduct a full-scale randomized controlled trial of the intervention compared to an educational, attention-control, or treatment-as-usual condition.

Inclusion Criteria:

Adolescents and families: Ninety adolescents between the ages of 12-17 years diagnosed with T1D and followed at the TCH Diabetes Care Center will be enrolled in the pilot study. At least one parent of each adolescent, self-identified as the primary caregiver most involved in diabetes care, will also be enrolled. When present, secondary caregivers involved in diabetes management will be invited (not required) to participate. Eligibility criteria will include: (1) T1D diagnosis for at least 12 months, to allow ample opportunity for adjustment to diabetes management, and (2) fluency in written and spoken English because assessment measures are not available in other languages.

Diabetes care providers: Five diabetes care providers in the TCH Diabetes Care Center (main hospital and/or satellites) will be enrolled as Resilience Promotion Providers to deliver the feedback intervention. Eligibility criteria will include: (1) Caseload of at least 20 adolescents with T1D, and (2) willing to participate in 2 training sessions, deliver the intervention to enrolled participants, and complete questionnaires.

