The following measures will be administered only as part of the baseline and follow-up assessment batteries. Adolescents will also complete the youth-report version of the DSMP-SR at baseline and follow-up to assess their perceptions of adherence. Behavioral outcomes include diabetes-related burden and family conflict. Burden will be assessed via the Problem Areas in Diabetes measures for adolescents (PAID-T) and parents (PAID-PR). The PAID-T has 26 items and the PAID-PR has 18 items, and both demonstrate good psychometric properties. Parents and youth will also complete the Diabetes Family Conflict Scale Revised (DFCS-R), a 19 item scale with good reliability and validity. To assess healthcare satisfaction, parents will complete three subscales of the Pediatric Quality of Life Inventory Healthcare Satisfaction Generic Module (PedsQL-HS), assessing their satisfaction with communication, inclusion of family, and how well the patient's emotional needs are addressed during the clinical encounter (13 items). Adolescents will rate their overall satisfaction with the patient-provider relationship on a 1-10 scale single item developed for this study, as there is no validated youth-report measure of satisfaction with care.

Clinical diabetes outcomes including glycemic control (HbA1c) and blood glucose monitoring frequency will be collected as part of routine care at each of the two study visits via blood assay and glucometer download, respectively.

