## Section G: Sample Size/Data Analysis

### G1. Sample Size

How many subjects (or specimens, or charts) will be used in this study?

Local: 90                  Worldwide: 90

Please indicate why you chose the sample size proposed:

This sample size will permit an ample number of families to experience the intervention and to give feedback that will permit us to refine the protocol for future research. Because gathering preliminary data on change in outcomes from pre- to post-intervention is the secondary aim of this pilot study, the sample is not powered for robust change analyses. However, trends can be identified from a sample of this size, which will inform future power analyses for a larger sample randomized controlled (intervention) trial.

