### G2. Data Analysis

Provide a description of your plan for data analysis. State the types of comparisons you plan (e.g. comparison of means, comparison of proportions, regressions, analysis of variance). Which is the PRIMARY comparison/analysis? How will the analyses proposed relate to the primary purposes of your study?

**Aim 1: Feasibility and Acceptability.** To evaluate the primary aims of this pilot study  $\zeta$  feasibility and acceptability of the intervention  $\zeta$  descriptive statistics (e.g., frequencies, means and standard deviations, medians and interquartile ranges) summarizing participant and provider ratings will be calculated.

**Aim 2: Preliminary Outcomes.** Because gathering preliminary data on change in outcomes from pre- to post-intervention is the secondary aim of this pilot study, the sample is not powered for robust change analyses. To explore change pre- to post-intervention, paired t-tests will be conducted for each outcome, comparing scores at baseline to follow-up. Change scores will be examined in relation to potential demographic or clinical covariates to explore whether individual, family, or provider characteristics need to be considered in the future refinement and evaluation of this intervention.

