## **Section K: Research Related Health Information and Confidentiality**

Will research data include identifiable subject information?

Yes

Information from health records such as diagnoses, progress notes, medications, lab or radiology findings, etc.

Yes

Specific information concerning alcohol abuse:

No

Specific information concerning drug abuse:

No

Specific information concerning sickle cell anemia:

No

Specific information concerning HIV:

No

Specific information concerning psychiatry notes:

No

Demographic information (name, D.O.B., age, gender, race, etc.):

Yes

Full Social Security #:

No

Partial Social Security # (Last four digits):

No

Billing or financial records:

No

Photographs, videotapes, and/or audiotapes of you:

No

Other:

No

At what institution will the physical research data be kept?

Baylor College of Medicine

How will such physical research data be secured?

All research data that is collected electronically will be entered in password-protected database and stored on a secure server, accessible only by the PI and study staff. Any research data collected via pencil and paper materials will be entered onto the same secure database and all hard copies will be stored in a locked filing cabinet in a locked office, accessible only to the PI and study staff. All study data (hard copies and electronic files) will be coded by being labeled with a study number and not with identifiable personal information. The only document linking participant names and IDs will be the signed consent/assent forms, and will be stored separately from study data and will be appropriately secured and accessible only to the PI and study staff.

At what institution will the electronic research data be kept?

Baylor College of Medicine

Such electronic research data will be secured via BCM IT Services- provided secured network storage of electronic research data (Non-Portable devices only):

Yes

Such electronic research data will be secured via Other:

No

Will there be anyone besides the PI, the study staff, the IRB and the sponsor, who will have access to identifiable research data?

No

Please describe the methods of transmission of any research data (including PHI, sensitive, and non-sensitive data) to sponsors and/or collaborators.

N/A

Will you obtain a Certificate of Confidentiality for this study?

No

Please further discuss any potential confidentiality issues related to this study.

N/A

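### The only planned post-intervention HbA1c is taken at the second intervention visit, so the glycaemic part of Hypothesis 2A is estimated only in families that attended that visit

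*Combined protocol and SAP*

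**What the plan says.** - **Collection (F2. Procedure).** The clinical outcomes are HbA1c and how often glucose is checked. The protocol says that these "will be collected as part of routine care at each of the two study visits via blood assay and glucometer download". No other collection point is given for either.
- **Intervention (F2. Procedure).** The intervention takes place at two successive clinic appointments, typically 3-4 months apart, and the second of these is called the second study visit. No visit window is set, and there is no rule for a missed visit.
- **Hypothesis (Section D).** Hypothesis 2A has two limbs over a 4-month period: better adherence and lower HbA1c. Adherence is measured by questionnaire (DSMP-SR) in the baseline and follow-up batteries.
- **Analysis (G2. Data Analysis).** "paired t-tests will be conducted for each outcome, comparing scores at baseline to follow-up". No analysis population, missing-data method or sensitivity analysis is given.
- **Design (F1).** "Ninety adolescents between the ages of 12-17 years diagnosed with T1D and followed at the TCH Diabetes Care Center will be enrolled". The design is single-arm, and "All participants will receive the intervention and will complete baseline and follow-up data".
- **Purpose of the change data (G1. Sample Size).** Change is the secondary aim and "the sample is not powered for robust change analyses", but its trends are to inform power calculations for a later randomized trial.
- **Other access to HbA1c.** Section D notes that "Youth with T1D are seen routinely in clinic every 3-4 months". Section K answers Yes to using "Information from health records such as diagnoses, progress notes, medications, lab or radiology findings, etc" as research data. No section says that the record will be used to obtain a follow-up HbA1c when the second visit does not take place.

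**The concern.** Outcome collection and intervention delivery share one appointment. A family that stops or never returns for visit 2 has no planned follow-up HbA1c, and the paired test then leaves it out without comment. The estimated change is therefore conditional on attendance.

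Keeping appointments is plausibly related to adherence and glycaemic control, though the documents do not quantify this. If the families lost are those whose HbA1c is flat or rising, the reported change leans towards improvement. The paired test gives no sign of it, and with a single arm there is no comparison group in which similar loss would show up. If the inflated change is then used as a planning effect for the randomized trial, that trial would be too small.

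**Working it through.** **1. Following the plan as written.** The post value is taken at the second study visit (F2), which is also the session-2 visit (F2). The paired t-test needs both values (G2). So no second visit means no pair. Nothing elsewhere in the protocol supplies a substitute value.

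**2. What attendance selects.** HbA1c drawn at visit 2 can reflect session 1 and the interval after it, but hardly feedback given at that same appointment. A family that had session 1 and missed visit 2 had the same prior exposure as an attender. The restriction thus selects by attendance and not by amount of intervention received.

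**3. Bias formula.** Let m be the share without a follow-up value, C the mean change in attenders and L the mean change in those lost. The mean over all families is (1 - m)C + mL, so the error from using C alone is C - [(1 - m)C + mL] = m(C - L): the share lost times the gap.

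**4. Inputs.** From the documents: N = 90. The protocol gives no loss rate, gap, SD of change or alpha, and has no power figure to reproduce. Assumed here: m = 10-30%, gap = 0.3-0.8 HbA1c points (those lost doing worse), SD of change 1.0 (also 1.3), two-sided alpha 0.05.

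**5. Size of the bias.** Smallest: 0.10 x 0.3 = 0.03 points. Largest: 0.30 x 0.8 = 0.24 points.

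**6. Effect on the paired test if the true mean change over all 90 is zero.** With n = 90(1 - m) and SE = SD/sqrt(n), the chance of a nominally significant improvement is about Phi(-1.96 + bias/SE), against 2.5% without bias.

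| Lost | Gap (points) | SD | n | Bias | SE | Chance of a false improvement |
|---|---|---|---|---|---|---|
| 10% | 0.3 | 1.0 | 81 | 0.03 | 0.111 | 4.6% |
| 20% | 0.5 | 1.0 | 72 | 0.10 | 0.118 | 13.3% |
| 20% | 0.8 | 1.0 | 72 | 0.16 | 0.118 | 27.3% |
| 20% | 0.5 | 1.3 | 72 | 0.10 | 0.153 | 9.6% |

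A noncentral-t calculation at 20% loss and a gap of 0.5 SD also gives 13%.

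**7. Precision is the smaller issue.** At 30% loss (63 pairs), the change detectable with 80% power rises from 0.30 to 0.36 SD of change, and the 95% confidence half-width from 0.21 to 0.25 SD.

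**The case against.** The strongest case against is that little depends on this. Aim 2 is secondary, the tests explore change, no alpha or success criterion is stated, and without a control group even a complete pre-post change cannot be attributed to the intervention. The protocol also supports retention: payment for the follow-up batteries, $5 per visit for bringing the meter and $12 per visit for travel. The loss rate, the gap and even the direction of the bias are assumed, and the mildest case above is close to nominal. All of this stands and limits the seriousness. It does not remove the bias from an estimate that G1 means to carry forward.

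A reader might also infer more than the text supports:

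- **That a postponed visit is lost.** F2 sets no window, so a late second visit is still the second visit and its HbA1c is collected.
- **That a family seen by a clinician outside the five trained providers is dropped.** The documents are silent on this, and a routine HbA1c would still be in the record.
- **That all of Hypothesis 2A is confined to attenders.** The adherence limb is survey-based, and nothing makes the follow-up battery conditional on session 2. It loses pairs only through survey non-response.
- **That F1 forecasts no attrition.** Its sentence answers a form question about group assignment and can be read as describing allocation only.

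**Conclusion.** The point holds for HbA1c. Followed as written, the plan yields a change estimated only in adolescents whose family attended the second study visit, and G2 has no rule that would reveal or correct this. The cause is as much G2's silence on missing data as the collection sentence in F2.

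The direction towards improvement rests on the assumption that non-attendance goes with worse control. The range of 0.03-0.24 HbA1c points rests wholly on the assumed loss and gap, and the error rates also on the assumed SD and alpha; they are illustrations, not predictions. This does not undermine the primary feasibility aim. The change should still be made, because the loss is largely avoidable at low cost and the estimate is meant to inform a later trial.

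**What to change.** **In F2:**
- For every adolescent who completed visit 1 (the first intervention visit, not a recruitment meeting), unless consent for record use is withdrawn, take the routine-care HbA1c from the chart closest to 4 months after visit 1. State a window, for example 3-6 months. Do this whether or not session 2 was delivered and whichever clinician was seen.
- Send the follow-up battery on a date counted from visit 1, also to families that stopped the intervention.

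**In G2:**
- Make the Aim 2 HbA1c result the change in all who started and have an available value.
- Report the number of pairs and the reasons for missing values.
- Show second-visit attenders as a secondary result, and do not label it a two-session effect, because the visit-2 HbA1c precedes any effect of session 2.

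**Cost and limits.** The change needs a wording amendment, a small amount of chart look-up and some extra survey links. Timing of the follow-up HbA1c becomes slightly more variable. Including families without session 2 should dilute the HbA1c change little, since their exposure before the measurement was the same. Meter downloads are not recovered, families with no clinic contact in the window remain missing, and survey non-response still affects the adherence limb.

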## Section G: Sample Size/Data Analysis

### G1. Sample Size

How many subjects (or specimens, or charts) will be used in this study?

Local: 90                  Worldwide: 90

Please indicate why you chose the sample size proposed:

This sample size will permit an ample number of families to experience the intervention and to give feedback that will permit us to refine the protocol for future research. Because gathering preliminary data on change in outcomes from pre- to post-intervention is the secondary aim of this pilot study, the sample is not powered for robust change analyses. However, trends can be identified from a sample of this size, which will inform future power analyses for a larger sample randomized controlled (intervention) trial.

### G2. Data Analysis

Provide a description of your plan for data analysis. State the types of comparisons you plan (e.g. comparison of means, comparison of proportions, regressions, analysis of variance). Which is the PRIMARY comparison/analysis? How will the analyses proposed relate to the primary purposes of your study?

**Aim 1: Feasibility and Acceptability.** To evaluate the primary aims of this pilot study  $\zeta$  feasibility and acceptability of the intervention  $\zeta$  descriptive statistics (e.g., frequencies, means and standard deviations, medians and interquartile ranges) summarizing participant and provider ratings will be calculated.

**Aim 2: Preliminary Outcomes.** Because gathering preliminary data on change in outcomes from pre- to post-intervention is the secondary aim of this pilot study, the sample is not powered for robust change analyses. To explore change pre- to post-intervention, paired t-tests will be conducted for each outcome, comparing scores at baseline to follow-up. Change scores will be examined in relation to potential demographic or clinical covariates to explore whether individual, family, or provider characteristics need to be considered in the future refinement and evaluation of this intervention.

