## F2. Procedure

**BASELINE & FOLLOW-UP OUTCOME ASSESSMENTS:** Following enrollment in the study, adolescents and parents will be e-mailed a link to complete the baseline assessment battery via secure web-survey. Participants will be encouraged to complete the battery at home prior to their next clinic appointment; for anyone unable to do so, a tablet computer will be available in the waiting room before the appointment. The assessment battery administered prior to the intervention visit will also be administered at follow-up to evaluate pre-post change.

Adolescent will self-report on the frequency of 12 resilience-promoting behaviors via the Diabetes Resilience Measure for Adolescents (DRM-A). The DRM-A is a self-report assessment of positive behaviors related to diabetes resilience for youth with T1D, such as perceived competence to manage the demanding T1D regimen, to adapt to the unpredictability of diabetes, and to seek help and support with diabetes challenges. This measure requires less than 5 minutes to complete. The DRM-A will be administered in the baseline and follow-up assessment batteries, and will also be administered as part of the intervention (See below).

Parents will rate adolescents' adherence to the diabetes regimen using the 24-item Diabetes Self-Management Profile Self-Report (DSMP-SR). The version appropriate to the adolescents' current diabetes regimen (conventional or intensive insulin regimen) will be administered. The DSMP-SR was developed to be minimally burdensome compared to adherence interviews and has demonstrated satisfactory psychometric properties. The DSMP-SR will be administered in the baseline and follow-up assessment batteries, and will also be administered as part of the intervention (See below).

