**INTERVENTION:** This intervention will be delivered at two consecutive ambulatory diabetes clinic appointments (typically scheduled 3-4 months apart). Prior to each appointment, youth and parents will each complete one intervention assessment questionnaire online (DRM-A and DSMP-SR, respectively - described above). The first intervention assessment will be included within the baseline outcome assessment battery described above; for the second study visit, it will be a single survey. For each intervention assessment, the adolescent will be asked to rate specific diabetes strengths, and the parent(s) will be asked to rate behavioral adherence to various diabetes management tasks. They will also be asked to indicate one positive behavior item that they wish to discuss with their diabetes care provider. A report (referred to as Resilience Profile) will be printed for the diabetes care provider, generated from the completed intervention assessments, which will highlight the top-rated positive behaviors from each questionnaire and the positive behavior items flagged for discussion. Diabetes care providers will be trained to review the Resilience Profiles with the adolescent and family during their clinical encounter, and to provide feedback that reinforces and builds upon the positive behaviors.

At follow-up, all participating participants and providers will be asked to complete a brief survey about their experiences in the study and requesting any feedback and recommendations to improve intervention delivery or content. The provider will also be asked about their experiences with integrating the intervention into routine care, perceptions of intervention feasibility, and impact on clinic flow.

**PROVIDER TRAINING:** Five diabetes care providers who volunteer to participate in this study will be trained to provide

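### For the DRM-A and parent DSMP-SR, the planned baseline-to-follow-up t-test leaves out a third score taken before visit 2, so families without follow-up drop out of the test even when that score exists

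*Combined protocol and SAP*

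**What the plan says.** Section F2 gives the DRM-A a double role: "The DRM-A will be administered in the baseline and follow-up assessment batteries, and will also be administered as part of the intervention". It says the same of the parent-completed DSMP-SR: "The DSMP-SR will be administered in the baseline and follow-up assessment batteries, and will also be administered as part of the intervention".

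The intervention part of F2 sets the schedule: "Prior to each appointment, youth and parents will each complete one intervention assessment questionnaire online". On the first of these, "The first intervention assessment will be included within the baseline outcome assessment battery described above". On the second, "for the second study visit, it will be a single survey". The two visits are "typically scheduled 3-4 months apart".

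Section G2, Aim 2, then says that "paired t-tests will be conducted for each outcome, comparing scores at baseline to follow-up". It adds that change scores will be examined against possible covariates. It names no analysis of the pre-visit-2 scores and no method for missing data. The only use the plan gives for the pre-visit-2 forms is to build the Resilience Profile for the provider.

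**The concern.** A paired t-test uses only families with both scores. A family that completes the pre-visit-2 form but not the follow-up battery contributes nothing, although its score after session 1 is on file. If families whose scores fell after session 1 are the ones who skip follow-up, the mean change among the remaining families is too favourable.

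These scales carry the adherence part of Hypothesis 2A (parent report) and the resilience part of 2B. Section G1 intends the observed trends to feed the power analysis of a later randomized trial, so an inflated change could make that trial too small. A two-point comparison also cannot show how much change appears after one session, which would help the refinement that G1 and G2 mention.

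**Working it through.** **Count of occasions.** Two batteries plus two intervention assessments, less the one contained in the baseline battery: 2 + 2 − 1 = 3. The t-test uses 2.

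**Inputs.** From the documents: 90 families (G1). G1 justifies this number by feasibility, so there is no power figure to reproduce. Assumed, because the documents are silent: 10-30% missing follow-up; correlations between occasions of 0.5-0.7, or 0.6 with baseline and 0.8 between the later two; two-sided alpha of 0.05.

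**1. Complete follow-up.** With correlation 0.6 the SD of change is √(2 − 2×0.6) = 0.894 score SDs, and the SE is 0.894/√90 = 0.0943. The unstructured three-occasion model gives the same contrast and the same SE.

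**2. Precision when follow-up is missing at random.** Take 20% missing (72 pairs) and all correlations 0.6.
- Paired SE: 0.894/√72 = 0.1054.
- Model: regressing follow-up on the two earlier scores gives coefficients of 0.6/1.6 = 0.375 each and residual variance 1 − 2×0.375×0.6 = 0.55. The weights on the two earlier means are −0.625 and 0.375, with variance 0.3906 + 0.1406 − 2×0.6×0.2344 = 0.25.
- Model variance: (0.55/72)×(1 + 0.2×2/68) + 0.25/90 = 0.01046, so the SE is 0.1023, which is 3.0% smaller.
- At 30% missing: 0.1127 against 0.1077, 4.4% smaller.
- If the later two scores correlate 0.8, the reductions are 5.8% (20% missing) and 8.8% (30% missing).

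**3. Bias when missingness depends on the baseline to pre-visit-2 change.** Assume no true change and log-odds of missing follow-up that rise by 0.5 or 1.0 for each SD by which that change is worse. With equal correlation ρ, the covariance of the two changes is 1 − ρ and the variance of each is 2(1 − ρ). The regression of full change on early change therefore has slope 0.5 for any ρ. The bias is half the selection shift in early change among families who stay. Multiplying by √n gives SE units.

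| Missing | Logit slope | Shift in early change (SD) | Bias, SD of change | Bias, SEs |
|---|---|---|---|---|
| 10% (n = 81) | 0.5 | 0.049 | 0.024 | 0.22 |
| 10% | 1.0 | 0.091 | 0.045 | 0.41 |
| 20% (n = 72) | 0.5 | 0.096 | 0.048 | 0.41 |
| 20% | 1.0 | 0.173 | 0.087 | 0.74 |
| 30% (n = 63) | 0.5 | 0.143 | 0.071 | 0.57 |
| 30% | 1.0 | 0.253 | 0.126 | 1.00 |

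A shift of 0.4 SE raises the chance of p<0.05 from 5% to Φ(−1.56) + Φ(−2.36) = 6.9%. A shift of 1.0 SE raises it to Φ(−0.96) + Φ(−2.96) = 17.0%.

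**4. What the model removes.** If every family has the pre-visit-2 score, the simulated model estimate has bias of at most 0.004 SD. If 50-80% of the families lost to follow-up also lack that form, about 0.01-0.065 SD remains at 20-30% missing.

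**5. Missingness driven by the pre-visit-2 level.** The covariance of that level with full change is r(2,3) − r(1,2), which is zero under equal correlations. Simulation agrees: with a true change of 0.20 score SDs, correlations 0.6 and slope 1, both estimates average 0.197-0.201. If the later two scores correlate 0.8, the covariance is 0.2. The paired mean then averages 0.217, 0.235 and 0.247 at 10%, 20% and 30% missing, while the model stays at 0.196-0.200.

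**The case against.** The planned test answers the hypotheses as written. Both 2A and 2B ask about change across the whole intervention, and the pre-visit-2 form exists to serve the intervention. Leaving it out of the outcome analysis can be a choice rather than an error, and G2 never says the scores will be thrown away; that follows only from the absence of any analysis. Aim 2 is secondary, G1 and G2 both say the sample is not powered for it, and no decision depends on p<0.05. This stands and limits the importance of the point.

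The size of the bias is wholly assumed, and under one plausible mechanism it is zero. That stands too. So does the limit on the remedy: section F2 pays $10 per person for each battery but nothing for the intervention questionnaires, so a family that skips the paid battery may have skipped the unpaid form as well. The other outcomes have no third questionnaire occasion and keep their exposure to lost follow-up.

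The objection does not show that the paired test is preferable for these two scales. The model keeps the same target, matches the test when data are complete, and uses scores already collected when they are not.

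A reader might go further and infer that Hypothesis 2A sets adherence and HbA1c over different periods, because HbA1c "will be collected as part of routine care at each of the two study visits" while adherence runs to the follow-up battery. The documents do not support this. They never date that battery, and the 4-month intervention period in section D, beside visits 3-4 months apart, is compatible with a follow-up close to visit 2. Pairing HbA1c with the pre-visit-2 adherence score would also replace the hypothesis with a question about change after one session.

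**Conclusion.** The point holds in a limited form. For two scales the plan collects three scores and analyses two, and the paired test drops any family without follow-up even when its pre-visit-2 score exists. The cost is nil for the main contrast if follow-up is complete. It is about 0.02-0.13 SD of change if 10-30% miss follow-up, missingness depends on the early change with a logit slope of 0.5-1.0 per SD, and correlations are equal at 0.5-0.7. It is zero if missingness depends only on the pre-visit-2 level and correlations are equal. The precision gain is small, roughly 3-4% of the SE at 20-30% missing with all correlations 0.6. A reader might take the bias as established; it is not, because the documents give no dropout rate, correlation or dropout mechanism.

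**What to change.** In G2, for the DRM-A and parent DSMP-SR only, replace the paired t-test with a linear mixed model on all three occasions: unstructured covariance, REML, every family with any score. Keep baseline to follow-up as the main contrast for Hypotheses 2A and 2B. Report baseline to pre-visit-2 and pre-visit-2 to follow-up as secondary contrasts, all with 95% confidence intervals. State how many families supplied each score, and how many without follow-up had the pre-visit-2 form. Keep paired t-tests for measures collected twice.

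This costs a few sentences and needs no new data or visits. The model assumes data are missing at random given the observed scores, which G2 should say, and it helps little for families who supply only a baseline score.
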